#### **7.4.3. Pregnancy**

- Details of all pregnancies in female subjects will be collected after the start of dosing and until the follow-up contact.

- If a pregnancy is reported then the investigator should inform GSK within 2 weeks of learning of the pregnancy and should follow the procedures outlined in Section 12.4.. Appendix 4.

Note: Subjects randomized in the epoetin beta pegol group should be advised to inform the investigator if they discover pregnancy in 7 weeks after the last dose of study treatment.

#### **7.4.4. Medical Device Incidents (Including Malfunctions)**

The medical devices are being provided for use in this study. The investigator is responsible for the detection and documentation of events meeting the definitions of incident or malfunction that occur during the study with such devices.

The definition of a Medical Device Incident can be found in Appendix 8 (Section 12.8.)

NOTE: Incidents fulfilling the definition of an AE/SAE will also follow the processes outlined in Section 7.4.1. and Appendix 6 (Section 12.6.) of the Protocol.

##### **7.4.4.1. Time Period for Detecting Medical Device Incidents**

- Medical device incidents or malfunctions of the device that result in an incident will be detected, documented and reported during all periods of the study in which the medical devices are available for use.
- If the investigator learns of any incident at any time after a subject has been discharged from the study, and such incident is reasonably related to a medical device provided for the study, the investigator will promptly notify GSK.

NOTE: The method of documenting Medical Device Incidents is provided in Appendix 8 (Section 12.8.).

##### **7.4.4.2. Follow-up of Medical Device Incidents**

- All medical device incidents involving an AE, will be followed until resolution of the event, until the condition stabilizes, until the condition is otherwise explained, or until the subject is lost to follow-up (as defined in Section 5.4.). This applies to all subjects, including those withdrawn prematurely.
- The investigator is responsible for ensuring that follow-up includes any supplemental investigations as may be indicated to elucidate as completely as practical the nature and/or causality of the incident.
- New or updated information will be recorded on the originally completed form "Medical Device Incident Report Form" with all changes signed and dated by the investigator.

##### **7.4.4.3. Prompt Reporting of Medical Device Incidents to GSK**

- Medical device incidents will be reported to GSK within 24 hours once the investigator determines that the event meets the protocol definition of a medical device incident.
- Facsimile transmission of the "Medical Device Incident Report Form" is the preferred method to transmit this information to the SAE contact information.
- The same individual will be the contact for receipt of medical device reports and SAEs.
- In the absence of facsimile equipment, notification by telephone is acceptable for incidents, with a copy of the "Medical Device Incident Report Form" sent by overnight mail.

**7.4.4.4. Regulatory Reporting Requirements for Medical Device Incidents**

- The investigator, or responsible person will comply with the applicable local regulatory requirements relating to the reporting of incidents to the IRB/IEC.

**7.4.5. Vital Signs/Height/Weight**

Systolic and diastolic blood pressure and pulse rate will be measured in sitting or semi-supine position after at least 5 minutes rest prior to clinical examination at each visit blood pressure and pulse rate.

One reading of blood pressure and pulse rate will be taken and recorded in the source document and the CRF. Height and weight will be measured at screening visit only.

**7.4.6. Electrocardiogram (ECG)**

12-lead ECGs will be recorded in supine position. The heart rate, PR, QRS, and QT (pre-corrected) intervals will be measured. QTcB should be calculated by machine or manually by designated staff at each site. The investigator determines whether the ECG data is assessable or not.

At screening, visit when an ECG is performed, two additional ECGs are required if initial ECG indicates prolonged QTc using the automated or manually calculated QTcB value. The average QTcB value of all three ECGs will be used to determine eligibility.

QTc exclusion criteria can be found in Section [5.2](#). Refer to SRM for further details.

**7.4.7. Clinical Laboratory Assessments**

All study-required laboratory assessments will be performed by a central laboratory with the exception of HemoCue Hgb. The results of each HemoCue Hgb must be entered into the subject's eCRF. Details are provided in the SRM.

All laboratory assessments, as defined in Table 16, must be conducted in accordance with the Laboratory Manual and Protocol Time and Events Schedule. Laboratory requisition forms must be completed and samples must be clearly labeled with the subject number, protocol number, site/center number, and visit date. Details for the preparation and shipment of samples will be provided by the central laboratory. Reference ranges for all parameters will be provided to the site by the central laboratory. Details of blood sampling (including the volume of blood to be collected) as well as procedures for processing, storage, and shipment of samples are provided in the SRM.

PK assessment of GSK1278863 is outlined in Section [7.5](#).

**Table 16      Laboratory Assessments**

Laboratory assessment	Parameter		
Hematology	Leukocyte count	RBC indices:	WBC count with Differential
	Platelet count	MCV	Neutrophils
	RBC count	MCH	Lymphocytes
	Reticulocyte count	MCHC	Monocytes
	Hemoglobin	RDW	Eosinophils
	Hematocrit		Basophils
Clinical chemistry	Sodium	AST	Bicarbonate
	Potassium	ALT	Inorganic phosphate
	Chloride	Creatinine	Glucose
	Calcium (total and albumin-corrected)	Total bilirubin	Direct/indirect bilirubin
	Albumin	Urea nitrogen	
	Total cholesterol	HDL cholesterol	LDL cholesterol
Iron parameters	Serum iron	Serum ferritin	Serum transferrin
	TIBC	UIBC	TSAT
	Hepcidin		
Urinalysis (ND subjects only)	Urine albumin	Urine creatinine	Urine albumin/creatinine ratio
Other laboratory tests	FSH 	Estradiol 	iPTH
	eGFR 	hCG (serum or urine) 	

1. Measured in female subjects only to determine the menopausal status (see Section 5.1.)
2. Calculated from serum creatinine using the Japanese Society of Nephrology-Chronic Kidney Disease Initiatives (JSN-CKDI) formula
3. Performed in females of childbearing potential: serum pregnancy test will be performed if urine pregnancy test is not feasible.

If additional non-protocol specified laboratory assessments are performed at the institution's local laboratory and result in a change in subject management or are considered clinically significant by the investigator (or subinvestigator) (e.g., SAE or AE or dose modification), the results must be recorded in the eCRF.

Refer to the SPM for appropriate processing and handling of samples to avoid duplicate and/or additional blood draws.

All laboratory tests with values that are considered clinically significantly abnormal during participation in the study should be repeated until the values return to normal or baseline. If such values do not return to normal within a period judged reasonable by the investigator (or subinvestigator), the etiology should be identified and the Sponsor notified.

#### 7.4.8. Ophthalmology

Ophthalmology exams will be performed by a study-designated ophthalmology specialist. Each assessment will include a comprehensive eye exam with at least the following components: measurement of best corrected visual acuity, intraocular pressure, an anterior aqueous chamber exam, and a fundoscopic exam. These exams will be used for assessment of ocular adverse events. Assessment results will be captured on worksheets which will be transferred to the eCRF. Additional details on the process for completing these assessments are provided in the SRM.

## 7.5. Pharmacokinetics

Blood samples for PK analysis of GSK1278863 will be collected from only subjects in the GSK1278863 group as outlined in Table 15, and the date and time of the last two study medication doses taken prior to blood sampling as well as the date and time of sampling must be recorded in the eCRF.

Blood PK analysis will be performed under the control of GSK Platform Technologies and Science-Drug Metabolism and Pharmacokinetics (PTS-DMPK)/Scinovo and GSK-Japan Bioanalysis, the details of which will be included in the SPM. Concentrations of parent GSK1278863 will be determined in blood samples using the currently approved analytical methodology. Raw data will be archived at the bioanalytical site.

Procedures for processing, storage, and shipment of samples are provided in the SRM.

## 7.6. Genetics

A blood sample will be collected for genetic analysis from consenting subjects. This sample can be collected on Day 1 once written informed consent has been obtained. Information regarding genetic research is included in Section 12.7. Appendix 7.

## 7.7. Patient Reported Outcome (PRO)

The patient reported outcome (PRO) [e.g., symptoms, severity, health-related QOL (HR-QoL), health status] will be assessed using several rating scales.

All questionnaires used in this study have been translated into Japanese and validated.

Specific instructions on how the subject is to complete the scales and the process for data entry are provided in the SPM.

### 7.7.1. SF-36

The SF-36 acute version is a general health status questionnaire designed to elucidate the patient's perception of his/her health on several domains, including physical functioning, role physical, bodily pain, vitality, social functioning, role emotional, mental health, and general health over the past seven days. The questionnaire contains 36 Likert type questions that ask the patient to recall how he/she felt during the past seven days.

### 7.7.2. EuroQol Health Utility Index (EQ-5D-5L)/EQ Visual Analogue Scale (EQ-VAS)

The EQ-5D-5L is intended to measure the general health status and health utility. The EQ-5D-5L consists of 2 concepts: self-reported health status consisting of five dimensions (mobility, self-care, usual activities, pain/discomfort, anxiety/depression) each of which can take one of five responses and self-rated health status on a visual analog scale (VAS), a thermometer-like line.

## 8. DATA MANAGEMENT

- For this study subject data will be entered into GSK defined CRFs, transmitted electronically to GSK or designee and combined with data provided from other sources in a validated data system.
- Management of clinical data will be performed in accordance with applicable GSK standards and data cleaning procedures to ensure the integrity of the data, e.g., removing errors and inconsistencies in the data.
- Adverse events and concomitant medications terms will be coded using MedDRA (Medical Dictionary for Regulatory Activities) and an internal validated medication dictionary, GSKDrug.
- CRFs (including queries and audit trails) will be retained by GSK, and copies will be sent to the investigator to maintain as the investigator copy. Subject initials will not be collected or transmitted to GSK according to GSK policy.

## 9. STATISTICAL CONSIDERATIONS AND DATA ANALYSES

A detailed description of any planned analyses will be documented in a RAP..Any deviations from the analyses described in the protocol will be documented in the RAP or the final study report.

### 9.1. Hypotheses

The primary objective of the study is to demonstrate the non-inferiority of GSK1278863 to epoetin beta pegol based on mean Hgb during the primary efficacy evaluation period (Weeks 40 to 52) in ND subjects, including Cohort 1 subjects (only ESA users) and Cohort 3 subjects (both ESA users and ESA non-users).

As a preliminary assessment, it will be confirmed whether the mean Hgb during the primary efficacy evaluation period in GSK1278863 group would be in target range (11.0-13.0 g/dL) at first. And then the following non-inferiority statistical hypotheses are to be tested at a one-sided significance level of 2.5% (i.e. two-sided significance level of 5%):

- $H_0$ : Treatment difference in mean Hgb during the primary efficacy evaluation period is -1.0 g/dL or less.
- $H_1$ : Treatment difference in mean Hgb during the primary efficacy evaluation period is greater than -1.0 g/dL.

Only when the primary endpoint achieves non-inferiority, statistical testing will progress to the principal secondary endpoint with a focus on superiority according to the step-down procedure. More specifically, the superiority of GSK1278863 to epoetin beta pegol in terms of target Hgb control in ND subjects, including Cohort 1 subjects (only ESA users) and Cohort 3 subjects (both ESA users and ESA non-users), is to be demonstrated at a two-sided significance level of 5% by testing the following statistical hypotheses:

- $H_0$ : The proportion of subjects whose mean Hgb during the primary efficacy evaluation period is within the target range (11.0-13.0 g/dL) is equal between the treatment groups.
- $H_1$ : The proportion of subjects whose mean Hgb during the primary efficacy evaluation period is within the target range (11.0-13.0 g/dL) is different between the treatment groups.

No hypothesis will be tested in PD subjects (Cohort 2).

## 9.2. Sample Size Considerations

### 9.2.1. Sample Size Assumptions

Assuming a non-inferiority margin of -1.0 g/dL, a treatment difference of 0.0 g/dL, and a standard deviation of 1.5 g/dL for mean Hgb during the primary efficacy evaluation period in ND subjects, two-sample t-test has at least 99% power at a one-sided significance level of 2.5% (i.e. two-sided significance level of 5%) with a sample size of 100 subjects per group. At planning the study, a dropout rate was assumed to be approximately 25%, 135 subjects were going to be randomized to each group. Given the results from previous non-inferiority studies of similar drugs (darbepoetin alfa, epoetin beta pegol, and peginesatide), the non-inferiority margin of -1.0 g/dL is set. Since an increase of 1.0 g/dL indicates improvement in anemia according to the guidelines for renal anemia in Japan, the non-inferiority margin of -1.0 g/dL may be the clinically acceptable largest difference in renal anemia.

While the present study is designed to ensure long-term safety data from 100 ND subjects, and the primary hypothesis test has at least 99% power to estimate the efficacy very precisely, non-inferiority can be statistically demonstrated with a minimum between-group difference of -0.582 g/dL.

During this study, the protocol has been amended (Amendment No.3) according to the change in starting dose for ND, ESA non-users. ESA non-users in Cohort 1 will be excluded from primary efficacy analysis according to this amendment. Additionally the protocol amendment has been made (Amendment No.4), in which the assumption of dropout rate after the start of study treatment was changed from 25% to 30% and 143 subjects per group (total 286 subjects) will be randomized.

Analysis populations for primary efficacy analysis and safety evaluation on ND subjects are illustrated below.

**Table 17 Primary Efficacy and Safety Analyses Populations for ND Subjects**

ND Subjects		Treatment Group	Starting Dose	Number of Randomized Subjects		Analysis Population		
Cohort 1	ESA non-users	GSK1278863	4 mg	82 subjects	169 subjects	286 subjects for safety analyses		
		Epoetin beta pegol	-					
	ESA users	GSK1278863	4 mg	87 subjects				
		Epoetin beta pegol	-					
Cohort 3	ESA non-users	GSK1278863	2 mg or 4 mg	≥80 ESA non-users will be randomized	117 subjects	204 subjects for primary efficacy analyses		
		Epoetin beta pegol	-					
	ESA users	GSK1278863	4 mg					
		Epoetin beta pegol	-					

Note: In Cohort 1, 169 ND subjects who met eligibility criteria were stratified by the current ESA therapy and baseline Hgb (ESA non-users:  $\geq 9.5$  g/dL,  $< 9.5$  g/dL, ESA users:  $< 11.0$  g/dL,  $\geq 11.0$  g/dL) and then randomized in a 1:1 ratio to GSK1278863 or epoetin beta pegol group. The same randomization strategy is used in Cohort 3.

When non-inferiority is tested in 204 ND subjects, this number of subjects ensures an enough power. This is because a power of at least 97% will be achieved in a population consisting of 140 subjects,

who will complete study on the condition of a dropout rate of approximately 30%, by the same assumptions and non-inferiority margin stated as above. In order to allow a subgroup analysis of the primary endpoint by the use of ESA in subgroups the sizes of which are equal as much as possible, at least 80 ND, ESA non-users are to be enrolled in Cohort 3.

For PD subjects, the sample size is based on the feasibility. Assuming a sample size of 38 subjects and a standard deviation of 1.5 g/dL, the half width of the 95% CI for mean Hgb during the primary efficacy evaluation period is 0.493 g/dL.

### 9.2.2. Sample Size Sensitivity

The power for the primary endpoint is shown according to treatment difference and standard deviation in Table 18 based on a population consisting of 140 subjects (70 subjects per group) who will complete study on the condition of a dropout rate of approximately 30%. This population is derived from 204 ND subjects, including Cohort 1 subjects (only ESA users) and Cohort 3 subjects (both ESA users and ESA non-users)

**Table 18 Power Sensitivity (70 Subjects Evaluated Per Group, Noninferiority Margin of -1.0, One-Sided Significance Level of 2.5%)**

Treatment Difference	Standard Deviation		
	1.25	1.5	1.75
0	99.7%	97.5%	91.2%
-0.1	98.8%	94.1%	85.6%
-0.2	96.4%	88.0%	76.6%
-0.3	90.8%	78.3%	65.2%

### 9.2.3. Sample Size Re-estimation or Adjustment

No sample size re-estimation is planned for this study.

## 9.3. Data Analysis Considerations

### 9.3.1. Analysis Populations

- All Screening Population

The All Screening Population consists of all subjects who are given subject number and whose data are collected, including demographics at screening.

- Intent-to-Treat (ITT) Population

The Intention-To-Treat Population consists of Cohort 1 subjects (only ESA users) and Cohort 3 subjects (both ESA users and ESA non-users) who are given randomization number with Hgb measurement at both baseline and at least one scheduled visits following the baseline. Subjects will be analyzed according to randomized treatment. This population will be the primary population for an assessment of non-inferiority.

- modified ITT (mITT) Population

The mITT Population consists of all ITT subjects who have at least one Hgb measurement during the efficacy evaluation period. Subjects will be analyzed according to randomized treatment. This population will be the primary population for an assessment of superiority.

- **Per-Protocol (PP) Population**

The PP Population consists of all mITT subjects who are not major protocol violators. Details will be defined in the RAP. This population will be used for efficacy sensitivity analyses.

- **Safety Population**

The Safety Population consists of all subjects who receive at least one dose of study treatment. Subjects will be analyzed according to the treatment received. This population will be used for safety analyses.

- **PK Population**

The PK Population consists of all GSK1278863-treated subjects from whom PK samples are collected and analyzed.

Additional populations may be defined in the RAP.

### **9.3.2. Interim Analysis**

No interim analysis is planned.

### **9.3.3. Adjustment for Multiplicity**

Adjustment for multiplicity will be applied to maintain an overall type I error rate of 5%. After a preliminary assessment, the primary endpoint will be evaluated to demonstrate the non-inferiority at a one-sided significance level of 2.5% (i.e. two-sided significance level of 5%). Only when the primary endpoint achieves non-inferiority, statistical testing will progress to the principal secondary endpoint with a focus on superiority. Since the process will follow step-down manner, a multiplicity adjustment for a two-sided significance level of 5% will not be needed according to a closed test procedure.

Other secondary endpoints, which will be evaluated on a complementary or exploratory basis, will be compared at a two-sided significance level of 5% without multiplicity adjustment.

Since Cohort 2 is a single-arm cohort, no testing will be performed to evaluate the efficacy in PD subjects.

## **9.4. Key Elements of Analysis Plan**

### **9.4.1. Primary Efficacy Analysis**

The primary endpoint, which is the mean Hgb during the primary efficacy evaluation period, will be analyzed to demonstrate the non-inferiority of GSK1278863 to epoetin beta pegol in ND subjects. MMRM will be used to estimate the mean Hgb during the primary efficacy evaluation period and its 95% CI by treatment groups. This model includes treatment groups, baseline Hgb, assessment visits, interaction terms between treatment groups and assessment visits, as well as interaction terms between baseline Hgb and assessment visit. As a preliminary assessment, it will be confirmed if the mean Hgb during the primary efficacy evaluation period in GSK1278863 group would be in target range (11.0-

13.0 g/dL) at first. This confirmation will be established if the lower and upper limit of 95% CI for the mean Hgb in GSK1278863 group would lie fully within target range (11.0-13.0 g/dL). In addition, the point estimate and 95% CI for the treatment difference (GSK1278863-epoetin beta pegol) in the mean Hgb during the primary efficacy evaluation period will be estimated. Non-inferiority will be established if the lower limit of the 95% CI is greater than -1.0 g/dL. Even if the 95% CI for the difference is completely negative (i.e. lies fully within the range -1.0 to <0 g/dL) non-inferiority would still be concluded on condition that the mean Hgb estimated in the GSK1278863 group is within the target range.

The primary efficacy population will be the ITT Population, and the analysis will be repeated in the mITT and PP Population to evaluate the robustness of the conclusion. The subgroup analysis by the current ESA therapy (presence or absence) will also be conducted.

Following sensitivity analyses will be conducted to assess robustness of the study result.

- If ND, ESA users in cohort 3 whose dose level was decreased by one step at Week 2 exist, sensitivity analysis excluding these subjects from primary analysis will be conducted.
- Sensitivity analysis to primary efficacy analysis for all ND patients in Cohort 1 and Cohort 3 will be conducted.
- If there are Hgb considered to be impacted by blood transfusion or marketed ESAs, sensitivity analysis excluding the Hgb values from the analyses of primary endpoint will be conducted.
- Analysis of covariance (ANCOVA) will be conducted as sensitivity analysis to MMRM. This model includes treatment group and baseline Hgb. The analysis population will be mITT population and the same analysis will be repeated in the PP population.
- A tipping point analysis based on multiple imputation will be conducted as sensitivity analysis to missing data assumption. This analysis explores a point where non-inferiority is not confirmed (tipping point) by changing assumption to missing data and repeating imputation. The analysis population will be ITT population and the same analysis will be repeated in the mITT and PP population.

Further details of sensitivity analyses will be provided in the RAP.

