### **6.3. Treatment Assignment**

The randomization schedule will be generated by GlaxoSmithKline (GSK) using the randomization system (Randall).

In Cohort 1 and Cohort 3 (ND subjects), subjects will be stratified by the current ESA therapy (ESA non-user or ESA user) and the Hgb level on Day 1 and randomized in a 1:1 ratio to one of the two treatment groups according to the randomization schedule. Randomization should precede the study treatment.

- GSK1278863 group
- Epoetin beta pegol group

In Cohort 2 (PD subjects), all eligible subjects will start treatment with GSK1278863 on Day 1.

Subjects will be assigned a randomization number by the Interactive Web Recognition System (IWRS). Once a randomization number has been assigned, it must not be re-assigned. Further details are provided in the Study Reference Manual (SRM).

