#### **9.4.2. Principal Secondary Efficacy Analysis**

The principal secondary endpoint, which is the proportion of subjects whose mean Hgb during the primary efficacy evaluation period is within the target range will be analyzed to demonstrate the superiority of GSK1278863 to epoetin beta pegol in ND subjects.

In the mITT Population, a logistic regression model including treatment group, baseline Hgb, and current ESA therapy (presence or absence) as covariates will be used to estimate the point estimate and 95% CI for the odds ratio (GSK1278863/epoetin beta pegol). This analysis will be performed to demonstrate the superiority at a two-sided significance level of 5%, conditional on the primary endpoint achieving noninferiority. Superiority will be established if the lower limit of the 95% CI for odds ratio is greater than 1.0.

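### The primary MMRM and the sensitivity ANCOVA omit current ESA therapy, a stratification factor for which the principal secondary model adjusts; the likely precision loss is small, but the missing-data assumption is stronger than it need be

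*Protocol*

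**What the plan says.** Section 6.3 describes the allocation of Cohorts 1 and 3: "subjects will be stratified by the current ESA therapy (ESA non-user or ESA user) and the Hgb level on Day 1". The synopsis and Section 4.1 give the Hgb cuts, 9.5 g/dL for ESA non-users and 11.0 g/dL for users.

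Section 9.4.1 fixes the primary model: "This model includes treatment groups, baseline Hgb, assessment visits, interaction terms between treatment groups and assessment visits", plus baseline Hgb by visit. For the sensitivity ANCOVA: "This model includes treatment group and baseline Hgb". ESA therapy enters the primary analysis only as a subgroup analysis.

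Section 9.4.2, for the principal secondary endpoint, specifies "a logistic regression model including treatment group, baseline Hgb, and current ESA therapy (presence or absence) as covariates".

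The boundary of the non-user Hgb strata appears in two forms. The synopsis and Section 4.1 put 9.5 g/dL in the lower stratum (≤9.5 against >9.5). The note to Table 17 puts it in the upper one (≥9.5 against <9.5) and continues "The same randomization strategy is used in Cohort 3".

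**The concern.** An analysis should normally condition on the factors used to stratify randomization. Here the protocol does so for the principal secondary endpoint and not for the primary one. Section 9.4.1 names the MMRM and ANCOVA terms itself and defers only further details of the sensitivity analyses to the RAP, so this is a choice the protocol makes.

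ESA status is also prominent in the design:

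- Eligible Hgb is 8.0 to <11.0 g/dL for non-users and 9.0 to 13.0 g/dL for users.
- The two groups start treatment under different rules.
- Section 4.5 reports more early Hgb rises above 2.0 g/dL than expected in non-dialysis non-users, and not in users.
- Because Cohort 1 non-users are excluded from the primary population, every non-user in it comes from Cohort 3, while 87 users come from Cohort 1.

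Two things could be at stake. If ESA status still predicts late Hgb after baseline Hgb is in the model, the CI is somewhat wider than necessary. And with about 30% dropout the estimate relies on the model's missing-data assumption. Without ESA status, missingness must be unrelated to it given arm, baseline and observed Hgb, which is a stronger assumption than the one needed if ESA status is included.

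**Working it through.** **1. The plan's own figures.** Section 9.2.1 states "Assuming a non-inferiority margin of -1.0 g/dL, a treatment difference of 0.0 g/dL, and a standard deviation of 1.5 g/dL".

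- At 100 per group it claims "at least 99% power at a one-sided significance level of 2.5% (i.e. two-sided significance level of 5%) with a sample size of 100 subjects". The noncentral t gives 99.7%.
- Smallest observed difference that still shows non-inferiority: −1 + t(0.975; 198) × 1.5 × √(2/100) = −1 + 0.418 = −0.582. This matches "non-inferiority can be statistically demonstrated with a minimum between-group difference of -0.582 g/dL".
- At 70 per group, Table 18 gives 97.5%, and the noncentral t gives 97.5%. The other cells agree to 0.1 point, except SD 1.75 at difference 0 (stated 91.2%, computed 91.9%), which has no bearing here.
- CI half-width at 70 per group: t(0.975; 138) × 1.5 × √(2/70) = 0.501 g/dL.

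**2. ESA mix.** The primary population is 87 + 117 = 204. With at least 80 of the 117 being non-users, users number from 87 to 87 + 37 = 124, so p runs from 87/204 = 0.43 to 124/204 = 0.61.

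**3. Precision.** Assumptions, not in the documents:

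- the stated SD of 1.5 is the residual SD of the model without ESA;
- g is the user/non-user gap at Weeks 40 to 52 given baseline Hgb;
- R² of ESA status on baseline Hgb is 0.33 to 0.41, from uniform or truncated-normal baselines within the eligible ranges.

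Residual variance with ESA = 1.5² − g² × p(1−p) × (1−R²).

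Example, g = 1.0, p = 0.608, R² = 0.378: 2.25 − 1.0 × 0.238 × 0.622 = 2.102. The SD is 1.450, the ratio 1.450/1.5 = 0.967, and the half-width 0.485.

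| Gap g (g/dL) | Half-width with ESA | Narrower by | Power at difference 0 | Power at −0.3 |
|---|---|---|---|---|
| no ESA term | 0.501 | – | 97.5% | 78.3% |
| 0.25 | 0.500 | 0.2% | 97.5% | about 78.4% |
| 0.5 | 0.497 | 0.8–0.9% | 97.7% | about 79% |
| 1.0 | 0.483–0.485 | 3.3–3.6% | 98.2% | about 81% |
| 1.5 | 0.459–0.464 | 7.5–8.4% | 98.9–99.0% | 84–85% |

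Simulation of an ANCOVA-type model (N = 204, stratified 1:1, 30% dropout, 2,000 runs per scenario) gave CI-width ratios of 0.993 at g = 0.5 and 0.968 at g = 1.0 with equal dropout. At g = 0 the ESA term widened the CI by 0.1% to 0.8%.

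**4. Missing data.** Same simulation, with the true difference at the margin of −1.0, half the subjects users, and users higher by g. In the adverse pattern, dropout is 20% in users and 40% in non-users on GSK1278863, and the reverse on control (30% overall).

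| g | Dropout | Bias without ESA | Type I without ESA | Bias with ESA | Type I with ESA |
|---|---|---|---|---|---|
| 0.5 | equal | +0.002 | 2.5% | +0.002 | 2.6% |
| 1.0 | equal | −0.002 | 2.1% | −0.002 | 2.6% |
| 0.5 | adverse | +0.034 | 3.2% | −0.009 | 2.0% |
| 1.0 | adverse | +0.093 | 5.2% | +0.006 | 2.7% |

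Type I error is one-sided, nominal 2.5%, and positive bias favours non-inferiority. The Monte Carlo error of a 2.5% rate is √(0.025 × 0.975/2000) = 0.35 point, so 3.2% alone is not clearly above nominal, whereas 5.2% is.

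Hand check: completing users are 0.8/(0.8 + 0.6) = 57.1% of the GSK1278863 arm and 42.9% of control, an imbalance of 0.143. Baseline Hgb absorbs about R² = 0.4 of it, leaving g × 0.143 × 0.6 = 0.043 at g = 0.5 and 0.086 at g = 1.0. The two models differ by 0.034 + 0.009 = 0.043 and 0.093 − 0.006 = 0.087, in agreement.

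**The case against.** A reader might infer that the primary CI is needlessly wide. The documents do not support that as a fact. It needs a residual ESA effect at Weeks 40 to 52 given baseline Hgb, and the protocol reports none. The Section 4.5 signal concerns Week 4. All subjects are titrated to one target range for nearly a year, and baseline Hgb, already in both models, absorbs part of the user/non-user contrast. Larger figures, up to a 13% cut in variance, come from assuming users end lower and a residual SD of 1.3. The protocol gives no direction for the gap, and its only SD is 1.5. This objection stands.

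A reader might also infer that non-inferiority would be unreliable. Under equal dropout, omission is neutral to slightly conservative. Bias arises only if dropout differs by both arm and ESA stratum and ESA status predicts late Hgb; reversing the dropout pattern would reverse its sign. The simulation has a single endpoint, so it probably exaggerates what an MMRM that also uses earlier Hgb would show. The planned tipping-point and ESA subgroup analyses address neighbouring questions, though neither replaces the covariate. The imputation model is not stated and is left to the RAP, so it cannot be faulted here.

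Finally, the two versions of the 9.5 g/dL boundary might seem to affect the primary result. They do not: both models use baseline Hgb itself, not the Hgb stratum.

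What remains is the unexplained difference between Sections 9.4.1 and 9.4.2, and a stronger missing-data assumption than necessary.

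**Conclusion.** The omission is real and is fixed in the protocol text. Its size is modest. On precision it is worth under 1% of CI width for a residual gap up to 0.5 g/dL and about 3.5% for 1.0 g/dL, with no gain and a cost under 1% if there is no gap. The 97.5% power is safe either way. These figures rest on SD 1.5, 70 per group, assumed baseline shapes and an assumed gap.

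The missing-data side is the stronger argument, but it is conditional. In the one adverse dropout pattern simulated, the bias was 0.03 to 0.09 g/dL toward non-inferiority, probably an upper range for that pattern, against a margin of 1.0 g/dL. Nothing here invalidates the trial. Making the change is worthwhile because it is almost free and aligns the primary analysis with the randomization. The boundary mismatch is a separate editorial correction that changes no planned estimate.

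**What to change.** In Section 9.4.1, and in the matching synopsis text for the ANCOVA, add current ESA therapy (user or non-user) and its interaction with visit to the primary MMRM, and add current ESA therapy to the ANCOVA, as Section 9.4.2 already does for the principal secondary model. The covariate is already collected for randomization. The cost is a few degrees of freedom: one parameter in the ANCOVA and one per modelled visit in the MMRM, so four if only Weeks 40, 44, 48 and 52 are modelled. The change should be made before the data are analysed.

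Separately, reconcile the non-user Hgb boundary in the synopsis, Section 4.1 and the Table 17 note to the one programmed in the IWRS. That is one line of text.
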